All subject assessments (screening through end of study) are in the schedule of events (section 3.2.1).

Study Drug Dosing Regimen:

Treatment Phase I: Subjects will be randomized to receive either a 750 mg undiluted slow IV push (100 mg/minute) of FCM or Placebo (15 ml of Normal Saline [NS]) IV push at 2 ml/minute on Day 0 and 7.

Treatment Phase II: Non-Responders from Phase I who qualify will receive an unblinded 750 mg undiluted slow IV push (100 mg/minute) of FCM on Day 0 and 7 of Phase II.

Long-Term Extension Phase III: Qualified subjects can potentially receive an unblinded single 750 mg undiluted slow IV push (100 mg/minute) of FCM when RLS symptoms worsen or reoccur.

Efficacy and Safety Follow-up:

Primary efficacy endpoint in **Treatment Phase I** is to determine the effectiveness of FCM in improving RLS severity associated with IDA. Effectiveness will be evaluated by:

- IRLSS score change from baseline to Day 42 with comparison between FCM vs. Placebo.
- CGI-I at Day 42.

Primary efficacy endpoint in **Treatment Phase II** is to determine the effectiveness of an additional unblinded single FCM treatment in improving RLS severity in non-responders from Treatment Phase I. Effectiveness will be evaluated by:

- IRLSS score change from baseline (For Phase II the "baseline" is established on Day 42 of Phase I) compared to Day 42 of Treatment Phase II
- - CGI-I at Day 42 in Treatment Phase II.

Secondary efficacy endpoints evaluated in both Treatment Phase's I and II are:

- Number of treatment responders at Day 42 (Treatment Phase I).
- Number of treatment responders at Day 42 (Treatment Phase II).
- IRLSS score change from Baseline (For Phase II the "Baseline" is established on Day 42 of Phase I) compared to Day 42 of Treatment Phase II.
- Number of Responders at Day 42 who receive FCM vs. Placebo in Treatment Phase I.
- Number of Responders at Day 42 in Treatment Phase II who receive FCM vs. Placebo in Treatment Phase I.
- CGI-I and PGI-I at each visit and percentage of subjects who are much or very much improved at Day 42. (Treatment Phase I and II).
- Change in IRLSS score from Day 42 (Treatment Phase I and II).
- Change from baseline brain MRI-determined iron concentration in the substantia nigra at or within 4 days after Day 42 (Treatment Phase I and II).
- Change in sleep quality, Medical Outcome Survey for Sleep (MOS), from Day 42 for Treatment Phase I and II subjects.

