3.0 RATIONALE AND OVERALL STUDY DESIGN

3.1 Rationale

Since Norlander ³¹ proposed the relationship between the administration of iron and the resolution of symptoms associated with RLS in 1953, many studies have been conducted to identify the mechanism for this relationship and the ideal treatment regimen. To date, studies suggest that the specific iron preparation, the amount of iron administered, and the timing of the administered iron may contribute to the magnitude and duration of the treatment effect. Nonetheless, few human clinical studies have investigated these treatment factors or the plausible mechanisms of action for RLS.

Studies of IV iron dextran suggest robust results in the control of RLS symptoms lasting two to 48 months.^{31,32} Given that iron dextran preparations are associated with significant risk of anaphylaxis, severe hypersensitivity reactions, and death, other IV iron formulations are now being investigated. Allen et al.³⁵ reported the results of a 46-subject trial that compared FCM 500mg X 2, FCM 1000 mg, and placebo.³⁵ Subjects treated with either dose of FCM demonstrated a reduction of RLS symptoms lasting for up to 24 weeks without additional need for alternative RLS medications. Currently, a 200-subject multicenter trial of FCM versus placebo is underway to expand upon these results in subjects with iron deficiency with or without IDA (NCT02397057). These studies utilize the FDA approved dose of 750mg X 2 that has been shown to be safe and effective in the treatment of IDA. This proposed trial will investigate the approved FCM 750mg X 2 dose in RLS-associated IDA patients and provide data on the long-term need for subsequent IV iron dosing in RLS subjects who respond to FCM therapy.

An altered iron homeostatic mechanism appears to be a primary component underlying RLS pathology and is reported to date as most prominently noted decreased brain iron in the substantia nigra.³⁰ This decreased brain iron is present in RLS patients even with normal peripheral iron stores. Systemic iron deficiency as seen with IDA appears to further accentuate this iron homeostatic imbalance, leading to a six-fold increase in RLS expression.³⁰ In this study, RLS subjects with IDA will undergo pre- and post-treatment brain MRI scans for comparative characterization of brain iron concentrations.

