6.4.1.5 Day 42 (End of Treatment Phase I)

The following should be assessed or obtained:

- Adverse events
- Concomitant medications
- IRLSS will be completed
- Investigator CGI-I Score

- Subject will independently complete the following:
 - ✓ Subject PGI-1 Score
 - ✓ Medical Outcome Study (MOS) Sleep Scale (range 0-100)
 - ✓ Hopkins RLS-Sleep Quality Questionnaire (HRSQ)
- Blood sample for hematology, iron indices, chemistries, and Vitamin D
- Physical exam
- Vital signs (sitting heart rate and blood pressure)
- Brain MRI will be scheduled
- Consent Non-Responders to participate in Treatment Phase II
- Re-educate **Responders** about the 46-week Long-term Extension (Phase III).

Subjects will be assessed by the Investigator and identified as either a treatment **Responder** or a **Non-Responder**. If the subject is a treatment **Non-Responder** in Phase I, the subject will be eligible to re-consent and enroll in Treatment Phase II (section 6.4.2). If the subject is determined to be treatment **Responder**, the subject will continue through into the Long-Term Extension Phase III (section 6.5) of the study.

For **Non-Responder** subjects that do not qualify for treatment Phase II due to laboratory parameters this will be the end of the subject's participation in the study. Subjects should be removed from the study and treated as deemed appropriate by the physician.

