8.4.2 Secondary Endpoints

Phase I and Phase II:

- Change in IRLSS score from Baseline to Day 42. (Treatment Phase I and II)
- IRLSS score change from Baseline (For Phase II the "Baseline" is established on Day 42 of Phase I) compared to Day 42 of Treatment Phase II.
- CGI-I and PGI-I at each visit and percentage of subjects who are much or very much improved at Day 42. (Treatment Phase I and II)
- Change in sleep quality (MOS Sleep) from Baseline to Day 42. (Treatment Phase I and II)
- Estimate the proportion of treatment non-responders in Phase I who respond to FCM in Phase II for each randomized treatment group. (Phase II only)
- Change in substantia nigra iron index from Baseline to Day 42. The index will be determined using measures of MRI relaxation rate (R2*) or Quantitative Susceptibility Mapping (QSM). (Treatment Phase I and II)
- Change in iron index (R2* or QSM) for thalamus and motor cortex from Baseline to Day 42. (Treatment Phase I and II).

Phase III:

- Change in IRLSS from Baseline to each scheduled assessment.
- Number of subjects who remained in the study to Week 52.

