8.5 Statistical Analyses of Efficacy

Categorical variables will be summarized with the number and percent of subjects in each treatment group with the characteristic. Quantitative variables will be summarized with the mean, median, standard deviation, minimum value, and maximum value. Baseline will be defined as the last value obtained before randomization.

Phase I

The treatment differences for the changing IRLSS score from Baseline to Day 42 will be assessed with the analysis of covariance with treatment as a fixed effect and baseline value as a covariate.

The treatment difference for the percentage of subjects who are much or very much improved at Day 42 as measured by the CGI-I will be assessed with the chi-square test.

Change from Baseline for IRLSS at Day 28, MOS at Day 42, and brain iron distribution at Day 42 will be assessed with the same method as IRLSS at Day 42. The percentage of subjects who are much or very much improved at Day 42 as measured by the PGI-I will be assessed with the chi-square test.

Phase II and III

All analyses will be descriptive.

For Phase II, the proportion of treatment **Non-Responders** in Phase I who respond to FCM in Phase II will be estimated and the IRLSS, CGI-I, PGI-I and brain iron distribution will be summarized at Day 42.

The Kaplan-Meier method will be used to estimate time from first dose of FCM to treatment intervention. Subjects in Phase III who discontinue the study before requiring treatment intervention will be censored on the day of the last contact with the Investigator.

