2. STATISTICAL METHODS

2.1 GENERAL CONSIDERATIONS

Analysis datasets will be produced according to CDISC standards. All study-collected data will be summarized in tables or graphs. Listing will be produced when appropriate and all ICH-required listings will be produced. In general, continuous variables will be summarized by number of subjects, mean, standard deviation (SD), median, minimum, and maximum values. Categorical variables will be summarized by number and percentage of subjects in each category.

In general, summary tables will present data by treatment group (for Phase I) and treatment phase.

Baseline definitions:

- Phase I: baseline (other than iron index) is the last non-missing value prior to receiving randomized study medication.
- Phase II: phase II baseline (other than iron index) is the last non-missing value prior to receiving unblinded FCM in Phase II.
- Phase I and Phase II: baseline for iron index measured by MRI is measured in screening.
- Phase III: phase III baseline is defined as Day 0 of Phase I for responders in Phase I and Day 0 of Phase II for responders in Phase II.

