The number (percentage) of treatment responders at Day 42 of Phase I and Phase II will be summarized by treatment group in Phase I, separately. The subjects who missing responder/non-responder classification will be considered as non-responder.

6.2.8 Phase I and Phase II: Change in substantia nigra iron index from baseline to Day 42

The actual value of substantia nigra iron index on baseline and Day 42, and change from baseline to Day 42 will be summarized via descriptive statistics by treatment group (for Phase I only) for each treatment phase.

Substantia nigra iron index will be measured using MRI relaxation rate (R2*) or QSM.

6.2.9 Phase I and Phase II: Change in thalamus and motor cortex iron index from baseline to Day 42

The actual value of thalamus and motor cortex iron index on baseline and Day 42, and change from baseline to Day 42 will be summarized via descriptive statistics by treatment group (for Phase I only) for each treatment phase, separately.

Iron index will be measured using MRI relaxation rate (R2*) or QSM.

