6.3 EXPLORATORY ANALYSES

6.3.1 Phases I and II: Vitamin D at each visit

The actual value of serum Vitamin D concentration on baseline, each post-baseline visit, and change from baseline to each post-baseline visit will be summarized via descriptive statistics by treatment group (for Phase I only) for each treatment phase.

A subject data listing of Vitamin D and phosphate for each visit will be provided.

6.3.2 Phases I and II: Change in thalamus and motor cortex iron index from baseline to Day 42 for other brain regions

The actual value of iron index in other brain regions (including caudate, putamen, nucleus accumbens, globus pallidus, subthalamic nuclei (STN), dentate and pulvinar) on baseline and Day 42, and change from baseline to Day 42 will be summarized via descriptive statistics by treatment group (for Phase I only) for each treatment phase, separately.

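### The Phase II MRI iron-index summary pools both Phase I arms and measures change from the pre-Phase I scan, so one row averages one-course and two-course changes

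*SAP*

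**What the plan says.** **Baseline.** The baseline list in SAP 2.1 gives most Phase II variables a baseline just before the unblinded FCM of that phase, but exempts the iron index. For that measure it states: "Phase I and Phase II: baseline for iron index measured by MRI is measured in screening". The schedule of events has a single screening column, ahead of Phase I, so this is the scan taken before any study drug.

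**Grouping.** In SAP 6.2.8 (substantia nigra) and 6.2.9 (thalamus and motor cortex), the Day 42 value and the change are to be "summarized via descriptive statistics by treatment group (for Phase I only) for each treatment phase". SAP 6.3.2 applies the same rule to "The actual value of iron index in other brain regions". Phase II is thus one undivided group.

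**Who is in Phase II.** SAP 1.3.1 admits Phase I non-responders from either arm who meet the ferritin and TSAT limits. All receive FCM on Days 0 and 7.

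**Protocol.** Section 3.1 says that subjects "will undergo pre- and post-treatment brain MRI scans for comparative characterization of brain iron concentrations". Section 8.4.2 lists "Change in substantia nigra iron index from Baseline to Day 42" for Phases I and II, with no baseline of its own for Phase II. The general rule in section 8.5 is: "Baseline will be defined as the last value obtained before randomization". A scan at the end of Phase I is already planned; for the Phase I Day 42 visit, section 6.4.1.5 states: "Brain MRI will be scheduled".

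**IRLSS, for comparison.** SAP 1.2.1 sets its Phase II baseline at Phase I Day 42, and SAP 6.2.1 and 6.2.2 summarise ex-placebo and ex-FCM non-responders separately.

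**The concern.** Between the screening scan and the Phase II Day 42 scan, an ex-placebo subject has had placebo and then one FCM course (2 × 750 = 1500 mg planned). An ex-FCM subject has had two courses (3000 mg planned). One mean over both groups does not show what the Phase II course did, and it does not show the cumulative change for any one exposure.

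SAP 1.2.1 describes Phase II as asking what additional FCM does in Phase I non-responders. In the same report, the IRLSS change for Phase II would span one course for everyone, while the brain-iron change would span one course for some subjects and two for others. Protocol 8.5.1 lists correlations between brain-iron change and RLS severity, so readers are likely to set the two side by side.

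The planned tables do not allow the missing quantity to be recovered. Phase I Day 42 iron values are summarised for all Phase I subjects, including responders who never enter Phase II. The SAP names a subject listing for IRLSS and one for Vitamin D and phosphate, but none for the iron index.

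**Working it through.** The plan states no figure for the iron index, so there is none to reproduce. The check has two parts.

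**1. What the Phase II row estimates.** Notation for the mean iron-index changes in subjects who enter Phase II:

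- a: ex-FCM, screening to Phase I Day 42 (first course)
- p: ex-placebo, screening to Phase I Day 42 (no iron given)
- bF: ex-FCM, Phase I Day 42 to Phase II Day 42 (second course)
- bP: ex-placebo, same interval (first course)
- w: ex-FCM share of Phase II

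| Summary | Quantity |
|---|---|
| Planned: pooled, from screening | w(a + bF) + (1 − w)(p + bP) |
| Pooled, from Phase I Day 42 | w·bF + (1 − w)·bP |
| By arm, from screening | a + bF and p + bP |
| By arm, from Phase I Day 42 | bF and bP |

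The planned row differs from the pooled Phase II change by w·a + (1 − w)·p. Two things follow:

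- The pooling causes the mixing. Moving the baseline alone would still average a second-course change with a first-course change. Splitting by arm alone makes each row uniform in exposure.
- The screening baseline is why even a split row would still contain the Phase I change. Isolating the Phase II course also needs the Phase I Day 42 scan.

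The documents give none of a, p, bF or bP, so the difference has no computable size.

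**2. How mixed the group might be (illustration only).** Inputs from SAP 1.3.3: 35 per arm, with 50% (FCM) and 15% (placebo) much or very much improved on the CGI-I. Assumptions:

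- These rates stand in for responder status.
- Nobody drops out.
- Every ex-placebo non-responder meets the laboratory criteria.
- A fraction e of ex-FCM non-responders meets them. The documents do not give e, so it is ranged.

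Ex-placebo: 35 × 0.85 = 29.75. Ex-FCM: 35 × 0.50 × e = 17.5e. Then w = 17.5e / (29.75 + 17.5e).

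| e | Ex-FCM in Phase II | Total | w |
|---|---|---|---|
| 1.00 | 17.5 | 47.25 | 0.370 |
| 0.50 | 8.75 | 38.5 | 0.227 |
| 0.25 | 4.375 | 34.125 | 0.128 |

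Under these assumptions the two-course share is about 13% to 37%.

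**The case against.** The strongest reply is that the screening baseline is deliberate and defensible. It is stated openly and agrees with the supplied protocol's general pre-randomisation baseline. It is also the one scan certain to precede all study drug. The synopsis allows the Day 42 scan up to 4 days after the visit, and Phase II dosing may start within 7 days of it, so some Phase I Day 42 scans could follow the first Phase II dose. Pooling Phase II over prior arm is also the SAP's habit for CGI-I, PGI-I and MOS. Screening against end of Phase II is still a comparison before and after treatment.

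Much of this stands. A reader might infer that the SAP breaks a protocol rule. It does not: Protocol 8.4.2 and 8.5 set no separate Phase II MRI baseline. (The SAP cites a protocol dated 4 September 2019 and the supplied one carries April 2016 dates, so this can be confirmed only for the supplied version. SAP section 9 lists no change on this point.) A reader might also call the pooled figure meaningless. It is a well-defined mean change since before the study, taken over subjects with different exposure.

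The reply does not remove the mixing. MOS is pooled too, but its Phase II change starts just before Phase II dosing and so spans one course for everyone. The iron index combines pooling with a pre-Phase I baseline. The scan-timing problem calls for a pre-dose check and is no reason to leave the arms merged.

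**Conclusion.** The point holds as a limit on interpretation. The Phase II iron-index row averages placebo-plus-one-course changes with two-course changes, and the planned output cannot separate them. This follows from the SAP's wording and needs no assumption beyond both arms contributing subjects to Phase II.

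The size is unknown. It is tempting to attach a percentage bias, but the documents do not support one. With all ex-FCM non-responders qualifying (w = 0.37) and no placebo change, assuming equal Phase II changes in both groups and a first-course change of 0 to 1 times that amount puts the excess at 0% to 37% of the Phase II change. Letting the second course instead add 0 to 1 times the first puts it at 37% (0.37/1.00) to 59% (0.37/0.63). Both are inventions about an unmeasured effect, which may be near zero in subjects selected for clinical non-response.

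Only the 13% to 37% two-course share is usable, and only as an illustration. The CGI-I rates come from patients without IDA, and the responder definition differs because an IRLSS of 10 or less qualifies by itself.

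The measures are secondary or exploratory, and SAP section 6 makes efficacy reporting descriptive. No primary endpoint or IRLSS result is affected. Low priority.

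**What to change.** 1. In SAP 6.2.8, 6.2.9 and 6.3.2, show the Phase II iron-index results by Phase I randomised arm, and label the change from screening as cumulative. This step alone removes the mixing.
2. Within each arm, also report the change from the Phase I Day 42 scan to the Phase II Day 42 scan. Restrict it to subjects whose Phase I scan precedes the first Phase II dose, and state how many are excluded. Add this second baseline to SAP 2.1.

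The cost is SAP wording, a check of scan against dosing dates (clock times where both fall on one day), and one extra block in three tables. Every scan needed is already in the schedule of events, and no planned summary is lost. Subjects without a usable pre-dose scan leave only the added block.

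The arm cells will be small: on the illustration above, about 30 ex-placebo and 4 to 18 ex-FCM at planned enrolment. Early termination, recorded in SAP section 9, is likely to make them smaller.

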2.1.1 Reporting Precision

Summary statistics will be presented to the following degree of precision, unless otherwise specified:

Statistics	Degree of Precision
Mean, Median, Quartiles,	One decimal place more than the raw data.
Standard deviation	Two decimal places more than the raw data.
Minimum, Maximum	The same as the raw data.
Percentage	One decimal place. A percentage of 100% will be reported as 100%. Percentages of zero will be reported as 0.

For weight and height, one decimal place will be used for summary statistics. Fractional numeric values will be presented with a zero to the left of the decimal point (for example, 0.12 – 0.30).

2.2 DEFINITIONS OF ANALYSIS POPULATIONS (ANALYSIS SETS)**2.2.1 ITT Population**

ITT population includes all the subjects who were randomized.

Summaries for ITT population will be based on the treatment group to which they were randomized.

2.2.2 Safety Population

Safety population includes all the subjects who were randomized and received at least one dose of study medication.

Summaries for safety population will be based on the actual treatment they received.

2.3 TIME WINDOWS FOR ANALYSIS

No visit window will be constructed. For analyses, only scheduled visits will be summarized in tables.

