6.6 Long-Term Extension Phase III Treatment

During Phase III, subjects could potentially receive additional, unblinded single FCM treatment if, at any time during this Phase, subjects report worsening of RLS symptoms (an increase >4 points on the IRLSS compared to the last evaluation captured for that subject). Blood samples will be taken prior to dosing to make certain the laboratory criteria are met (ferritin <300 ng/mL and a TSAT <45%). Subjects will receive a single FCM 750 mg undiluted slow IV push at 100 mg/minute. On Day 14 and 42, subjects will have a serum phosphate assessed. The subject will have a RLS symptoms (IRLSS and HRSQ) and adverse event assessment on Day 28 and 42 Days post dose by phone. No additional treatment will be allowed after the Week 46.

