6.7 Laboratory Assessments

Serum samples for laboratory analyses must be obtained at all appropriate visits and will be analyzed by the laboratory. All serum laboratory results will be provided to the physician for review and assessment. If the Investigator wishes to obtain a follow-up of an abnormal laboratory test, this test may be obtained after notification to the Sponsor. If a subject's phosphorous is below the LLN at the end of study participation the subject should return, as directed by the Investigator, for repeat phosphorous laboratory tests until the value is back WNL.

Hematology:	Hgb, Hct, RBC, WBC, MCV, MCH, MCHC, RDW, platelets, differential
	count, and reticulocyte count.

- Iron indices: serum iron, serum ferritin, and total iron binding capacity (TIBC), and percentage serum transferrin saturation (TSAT).
- Chemistry: sodium, potassium, chloride, BUN, creatinine, albumin, alkaline phosphatase, total bilirubin, gamma-GGT, AST, ALT, LDH, calcium, phosphorus, glucose, bicarbonate, and magnesium.

Other: urine pregnancy (if indicated), other metals (serum copper and zinc), 1,25 dihydroxy Vitamin D (1,25 [OH]₂D); 25 hydroxy Vitamin D (25OH-D) and erythropoietin.

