In **Treatment Phase III**, responders from either Treatment Phase I or Treatment Phase II will continue through into this 46-week long-term extension phase of the study, and be monitored and assessed by phone for RLS symptoms (IRLSS and HRSQ) and adverse events on Weeks 15, 25, 34, 43 and 52 (final follow-up visit) from treatment Phase I Day 0. During Phase III, subjects may receive additional unblinded treatments (i.e. a single FCM 750 mg undiluted slow IV push at 100 mg/minute) if at any time the subject reports worsening of RLS symptoms (an increase > 4 points on the IRLSS compared to the last evaluation captured for that subject) and laboratory criteria are met (ferritin < 300 ng/mL and a TSAT $< 45\%$). No additional treatment will be allowed after the Week 46. A final face-to-face study visit will occur on Week 52. If a clinic visit is not possible, final evaluation will be completed by phone.

The Schedule of Events for Phases I, II and III are presented as Table 1.1 and Table 1.2

Table 1.1 Schedule of Events Treatment Phase I and Treatment Phase II

STUDY VISIT PROCEDURES	SCREENING	Treatment Phase I and Treatment Phase II				
	-14	DAY 0	DAY 7+1	DAY 14+3	DAY 28+3 (PHONE CONTACT)	DAY 42+3
Informed Consent	X					X**
Eligibility	X	X				X
Medical History, including prior iron therapy	X	X				
RLS History	X	X				
D/C oral iron products	X					
Site contact IRT	X					
Physical exam	X					X
Vital Signs	X	X	X			X
Height and Weight without shoes	X					
CHDQ	X					
HTDI	X					
IRLSS	X	X			X	X
HRSQ		X				X
CGI-I						X
PGI-I						X
MOS Sleep Scale		X				X
Hematology	X	X	X	X		X
Iron Indices	X	X	X	X		X
Chemistry	X	X	X	X		X
Vitamin D		X	X	X		X
Erythropoietin		X				X
Trace Element		X				
Urine Pregnancy test	X					
Study Drug		X	X			
Brain MRI	X					X
Concomitant Meds	X	X	X		X	X
Adverse Events		X	X		X	X

** All Subject will be consented to participate in Treatment Phase II prior to any study procedures being completed

Table 1.2 Schedule of Events Long-Term Extension Phase III

STUDY VISIT PROCEDURES	Week 15 Phone Contact	Week 25 Phone Contact	Week 34 Phone Contact	Week 43 Phone Contact	Week 52 EOS
IRLSS	X	X	X	X	X
HRSQ	X	X	X	X	X
MOS / PGI-I					X
Concomitant Meds	X	X	X	X	X
Adverse Events	X	X	X	X	X
Physical Exam / VS	See protocol Section 6.6 for procedures for additional FCM dosing				
Iron Indices / Chemistries / Hematology					X
FCM Dosing					

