6.2.10 Phase III: Change in IRLSS total score from baseline to each visit

The actual value of IRLSS total score on baseline and each scheduled visit (i.e. Weeks 15, 25, 34, 43 and 52 via phone contact), and change from baseline to each scheduled visit will be summarized via descriptive statistics.

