7.2 CLINICAL LABORATORY PARAMETERS

Laboratory assessments include hematology, clinical chemistry/ phosphorus, and iron indices:

- Hematology: Hgb, Hct, RBC, WBC, MCV, MCH, MCHC, RDW, platelets, differential count and reticulocyte count.
- Clinical chemistry: sodium, potassium, chloride, BUN, creatinine, albumin, alkaline phosphatase, total bilirubin, gamma-GGT, AST, ALT, LDH, calcium, phosphorus, glucose, bicarbonate and magnesium.
- Iron indices and Phosphorus: serum iron, serum ferritin, and total iron binding capacity (TIBC), percentage serum transferrin saturation (TSAT).

- Other: urine pregnancy (if indicated), other metals (serum copper and zinc), 1,25 dihydroxy vitamin D, 25 hydroxy Vitamin D (25OH-D) and erythropoietin.

All laboratory parameters will be presented in standard units. The actual value and change from baseline will be summarized by visit and treatment group (for Phase I only) using descriptive statistics.

The number and percent of subjects with treatment-emergent potentially clinically significant (PCS) laboratory values after baseline will be summarized by visit and treatment group (for Phase I only) for each phase. The denominator is all subjects with normal baseline and at least one post baseline assessment in the safety population of that phase and the numerator is the number of subjects with PCS (i.e., meets Grade III or Grade IV toxicity criteria from the National Cancer Institute Common Terminology Criteria) at post-baseline.

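### Phosphate drawn after a Phase III re-dose is probably left out of the laboratory tables under SAP 2.3, and at best has no defined place in them

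*SAP*

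**What the plan says.** SAP 2.3 sets no visit windows and then states: "For analyses, only scheduled visits will be summarized in tables". The term is not defined. For laboratory data SAP 7.2 says: "The actual value and change from baseline will be summarized by visit and treatment group (for Phase I only) using descriptive statistics". The table of potentially clinically significant (PCS) values, meaning Grade III or IV, is also organised by visit, for each phase. Its numerator is described only as a post-baseline value reaching those grades.

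Protocol 6.6 allows a further FCM dose in Phase III if "at any time during this Phase, subjects report worsening of RLS symptoms", subject to laboratory criteria and with an end date: "No additional treatment will be allowed after the Week 46". It then requires: "On Day 14 and 42, subjects will have a serum phosphate assessed".

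On Phase III visits, SAP 6.2.10 (about the IRLSS) refers to "each scheduled visit (i.e. Weeks 15, 25, 34, 43 and 52 via phone contact". SAP Table 1.2 has the same five columns and marks chemistry at Week 52. For re-dosing it says "See protocol Section 6.6 for procedures for additional FCM dosing".

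Protocol 6.7 lets the investigator follow up any abnormal result after notifying the sponsor. Subjects with low phosphorus at the end of participation are to come back "for repeat phosphorous laboratory tests until the value is back WNL".

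Three other provisions bear on the point. SAP 2.1 promises tables or graphs of everything collected. SAP 6.3.1 provides a phosphate listing under a heading limited to Phases I and II. SAP 7.1.1 makes hypophosphatemia an adverse event of special interest (AESI), found by MedDRA terms.

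**The concern.** Phosphate is the only laboratory test that Protocol 6.6 names after a re-dose, and low phosphate is an AESI in the SAP. These two draws are the trial's direct laboratory evidence on phosphate after a further FCM dose. Their dates depend on when the subject worsens, so they belong to no fixed study week. A rule that admits only scheduled visits, applied to tables built by visit, could leave Week 52 as the only Phase III phosphorus row.

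At stake is whether the report can describe phosphate after re-treatment. A subject could have a Grade III value two weeks after the re-dose, recover by Week 52, and not appear in the Phase III PCS table. Safety analysis is descriptive and there is no data safety monitoring board, so these tables are the main place where such a value would be seen.

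**Working it through.** The plan states no figure on this point, so the check is one of timing and text.

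**Timing.** Inputs: draws at Day 14 (2 weeks) and Day 42 (6 weeks) after the re-dose, and last re-dose at Week 46 (Protocol 6.6); charted Phase III chemistry at Week 52 (SAP Table 1.2). Assumptions: weeks count from Phase I Day 0, and the earliest re-dose is Week 7, just after the Week 6 responder assessment.

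For a re-dose at week w, Day 14 falls at w + 2, Day 42 at w + 6, and the gap to Week 52 is 52 − w.

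| Re-dose week | Day 14 at week | Day 42 at week | Weeks from re-dose to Week 52 |
|---|---|---|---|
| 7 | 9 | 13 | 45 |
| 15 | 17 | 21 | 37 |
| 25 | 27 | 31 | 27 |
| 34 | 36 | 40 | 18 |
| 43 | 45 | 49 | 9 |
| 46 | 48 | 52 | 6 |

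- Day 14 at Week 52 needs w = 52 − 2 = 50, which is past the Week 46 limit. It never happens.
- Day 42 at Week 52 needs w = 52 − 6 = 46. This is the single overlap.
- Some re-doses put a draw on another charted week (w = 13 puts Day 14 at Week 15, for example), but those contacts are by phone and have no chemistry entry.

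A subject re-dosed once before Week 46 has 2 + 1 = 3 required phosphorus time points after the re-dose, of which the charted visits hold 1. Even that one may be missing: Protocol 6.5 lets the final evaluation be done by phone, with blood tests then only recommended.

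**Text: are the re-dose draws scheduled visits?**

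- *Likelier reading: no.* SAP 6.2.10 equates the Phase III scheduled visits with five study weeks. Table 1.2 has the same five columns. A programmer applying 2.3 and 7.2 would produce a Week 52 row only.
- *Generous reading: yes.* The protocol requires the draws and Table 1.2 points to Section 6.6. But SAP 7.2 gives them no visit label. SAP 2.1 also fixes the Phase III baseline at Day 0 of Phase I or Phase II, so change from baseline would not isolate the re-dose. They would be admitted in principle with nowhere to go.

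**Text: unscheduled tests.** Follow-up and repeat tests under Protocol 6.7 have no planned date, so SAP 2.3 keeps them out of tables in every phase. The end-of-participation repeats follow a low value that is usually already tabulated. What is lost is mainly recovery, and occasionally a worse grade on a later draw.

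**Text: other outputs.** The 6.3.1 listing does not extend to Phase III. The AESI table reads reported terms, and under Protocol 7.1 a laboratory value becomes an adverse event only when it is judged a clinically significant worsening.

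**The case against.** The best case against the point is that exclusion is inferred, not stated. The term is undefined, the five-week list comes from an efficacy section, the draws are mandatory, the schedule refers to Section 6.6, and SAP 2.1 promises to summarise all collected data. The PCS numerator in SAP 7.2 carries no scheduled-visit limit of its own. This stands to the extent that exclusion cannot be called certain. It does not rescue the plan: the general promise in 2.1 conflicts with the specific rule in 2.3, and the cross-reference creates no analysis time point.

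A second objection is that clinically important low phosphate would be reported as an adverse event and reach the AESI and severity tables. That route is real, but it depends on judgement. The documents are also inconsistent on who sees phosphorus. Protocol 5.2 blinds study personnel to it throughout the study, Protocol 5.2.1.1 has unblinded personnel assess it, and Protocol 6.7 sends all serum results to the physician.

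Third, keeping ad hoc repeats out of by-visit means is ordinary practice. That is accepted, and the fix leaves it alone.

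A reader might also infer that re-dosed subjects have the highest FCM exposure in the trial. The documents do not support this as a general statement. An FCM responder re-dosed once has received 2 × 750 + 750 = 2250 mg. A placebo responder re-dosed once has received 750 mg. A Phase I FCM non-responder who completes Phase II dosing has received 4 × 750 = 3000 mg without any Phase III dose.

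**Conclusion.** The point holds as a defect of specification with a probable loss of safety information. On the likelier reading, every Day 14 phosphate value after a re-dose is outside the Phase III laboratory and PCS tables, as is every Day 42 value except after a Week 46 re-dose. On the generous reading these values have no defined row. Week 52 chemistry, 6 to 45 weeks after the re-dose, is not a substitute for the Day 14 value. The exclusion of unscheduled tests is clear, but its effect on Grade III/IV counts is limited.

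Two stronger conclusions are not supported. The SAP does not expressly bar every post-re-dose value. Nor would low phosphate necessarily go unreported: the values remain in the database, and reported adverse events are still tabulated.

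The size cannot be given as a number of subjects. The SAP says the study ended early, and neither document gives the number re-dosed. The timing rests on the Week 7 assumption and a common week count. The protocol at hand bears April 2016 dates while the SAP cites one dated 4 September 2019, so the conclusion also assumes that Sections 6.6 and 6.7 did not change between them. The efficacy analyses are not affected.

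**What to change.** 1. In SAP 2.3 and 7.2, base Grade III/IV PCS counts on all post-baseline values in each phase, including post-re-dose, unscheduled and repeat tests. Keep the scheduled-visit rule for by-visit means.
2. Define Day 14 and Day 42 after a re-dose as Phase III analysis time points. Add one table of phosphate at those points for re-treated subjects, with change from the last available phosphate before the re-dose and n (%) at Grade III/IV.
3. Extend the phosphate listing to Phase III, define what a scheduled visit is, and reconcile SAP 2.1 with 2.3.

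The cost is SAP wording, one table and one listing, built from draws that the protocol already requires. PCS rates may look slightly less favourable. One limit remains: Protocol 6.6 explains the pre-dose sample only by ferritin and TSAT. If phosphate is not measured in it, the reference could be as old as the Day 42 value of Phase I, which is up to 46 − 6 = 40 weeks before a Week 46 re-dose. The table should therefore show how old the reference value is.
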